5.4.4 Implementation of dose escalation decisions

To implement dose escalation decisions, the available toxicity information (including adverse events and laboratory abnormalities that are not DLTs), the recommendations from the BLRM (Part 1 only), and the available PK and PD information will all be evaluated by the Investigators and Novartis study personnel (including the study physician and statistician) during a dose decision meeting by teleconference. The meeting will, at least, be composed of all investigators

who have included patients in the cohort for evaluation and a representative of the sponsor. The final dose escalation decisions will be made between the sponsor and the study investigators. Drug administration at the next higher dose level may not proceed until the investigator receives written confirmation from Novartis indicating that the results of the previous dose level were evaluated and that it is permissible to proceed to a higher dose level.

5.4.5 Intra-patient dose escalation

Part 1

Enrolled patients who tolerate the assigned doses of branaplam and continue to extended treatment *may* be escalated to a higher dose once this higher dose has been deemed safe in other patients as determined by BLRM with EWOC. This decision will be made on a patient by patient basis based on PK accumulation data from that patient, review of all available safety data, and PD response. Each time the dose will be escalated for a patient, a new cycle will have to be started again as described in Table 7-2.

Data at the new dose level will not be formally included in the statistical model describing the relationship between dose and occurrence of DLT. However, these data will be incorporated into the clinical assessment of safety when escalation to a new dose level is considered for the study.

Whenever a patient experiences a DLT, treatment with the study drug will be interrupted and the toxicity will be followed up as described in Section 5.4.6.

Table 5-6 Criteria for defining dose-limiting toxicities during dose escalation –
Part 1

TOXICITY	DLT CRITERIA
Blood and lymphatic	Anemia CTCAE Grade ≥ 3
system disorders	Neutrophil count CTCAE Grade ≥ 4
	Febrile neutropenia CTCAE Grade ≥ 3
	Platelet count CTCAE Grade 3 or Grade 2 accompanied by clinically significant bleeding
	Platelet count CTCAE Grade ≥ 4
Gastrointestinal disorders	Diarrhea CTCAE Grade 3 ≥ 72 hrs., or dehydration > 5% requiring therapy
	Diarrhea CTCAE Grade 4,
	Vomiting CTCAE Grade 3 ≥ 72 hrs., despite the use of anti-emetic therapy
	Vomiting CTCAE Grade 4, despite the use of anti-emetic therapy
	Evidence of oral, peri-anal or gastric mucositis characterized by the presence of ≥ 2 of the following within 1 week;
	Diarrhea CTCAE Grade 3 ≥ 48 hrs.
	Vomiting CTCAE Grade 3 ≥ 48 hrs., despite the use of anti-emetic therapy
	Ulceration CTCAE Grade 2 ≥ 48 hours
	Haemorrhaging CTCAE Grade 2 ≥ 48 hours

TOXICITY	DLT CRITERIA
Investigations	Bilirubina CTCAE Grade 2 for > 7 consecutive days
	Bilirubina CTCAE Grade ≥ 3
	AST or ALT ≥3 ULN in conjunction with blood bilirubin ≥ 2 x ULN of any duration
	AST or ALT \geq 5 x ULN in conjunction with blood bilirubin \geq 2 x ULN of any duration, for patients with elevated AST, ALT, or blood bilirubin at baseline
	AST or ALT CTCAE Grade 3 for > 7 consecutive days AST or ALT CTCAE Grade 4
	Serum alkaline phosphatase CTCAE Grade 4 > 7 consecutive days
	Serum Creatinine Grade 2 for more than 7 days Serum Creatinine Grade ≥ 3
	Serum lipase and/or serum amylase CTCAE Grade 3 > 7 consecutive days with clinical signs or symptoms of pancreatitis
	Serum lipase and/or serum amylase (symptomatic and asymptomatic) CTCAE Grade 4
Other toxicities	Any other CTCAE Grade ≥ 3 toxicity except: An AE must be clinically significant to be defined as DLT: lymphopenia, study drug-related fever and electrolyte abnormalities (including K, Na, Cl, HCO3, Mg, Ca, PO4) that are ≤ CTCAE grade 3 abnormalities will not be considered a DLT unless clinically significant. Single incident of allergy to study drug will not be defined as DLT
	Any adverse event or serious adverse event that is suspected to be related to the study drug per investigator assessment and which leads to a temporary interruption of treatment with study drug for more than 14 consecutive days from the day of the first missed dose.

Patients may receive supportive care as per local institutional guidelines. Optimal therapy for vomiting or diarrhea will be based on institutional guidelines, with consideration of the prohibited medications listed in this protocol.

When there is ambiguity about whether an AE is related to the underlying disease as opposed to the study drug, the most conservative approach will be taken and the AE will be considered as study drug related.

5.4.6 Follow up for toxicities

For patients who do not tolerate the protocol-specified dosing schedule due to drug related toxicities, temporary dose interruptions are permitted.

If the patient has experienced evidence of clinical benefit and in the opinion of the investigator it is in the best interest of the patient to remain on study, then following discussion and agreement with the sponsor, the patient may continue on study treatment.

The guidelines in Table 5-5 should be applied. Novartis study team can at all times during the study ask the investigator to discontinue the treatment, also for reasons not specified in the

Table 5-5. For example, in case emerging PK data for an individual patient is showing higher exposure than anticipated, the investigator could be asked by Novartis study team to lower the dose, even if no toxicity has been observed. Any dose modification must be recorded on the Dosage Administration Record CRF.

Novartis

The below guidance for interruption of study treatment is applicable when there is no clear clinical explanation for the toxicity other than possibly due to study treatment. It may not necessarily apply to abnormalities assessed by the Investigator as associated predominantly with the underlying disease or intercurrent illness. Such cases should be discussed with the Novartis medical team.

Table 5-7 Criteria for interruption and re-initiation of branaplam treatment for AE possibly related to study medication

possibly related to study medication	
Worst toxicity CTCAE Grade ^a	7 days post dose administration (including day of administration)
Blood and lymphatic sys	stem disorders
Anaemia	
Grade 1	Maintain dose
Grade 2 or higher	Suspend dose until resolved to Grade ≤ 1 or baseline
	If not resolved after 14 days then discontinue of study treatment
Neutropenia (ANC)	
Grade 1	Maintain dose
Grade 2	Maintain dose
Grade 3 and Grade 4	Suspend dose until resolved to Grade ≤ 1 or baseline
	If not resolved after 14 days then discontinue of study treatment
Febrile neutropenia	
Grade 3	Suspend dose until resolved
	If not resolved after 14 days then permanently discontinue of study treatment
Grade 4	Suspend dose and discontinue of study treatment
Thrombocytopenia	
Grade 1	Maintain dose
Grade 2 or higher	Suspend dose until resolved to Grade ≤1 or baseline
	If not resolved after 21 days , then permanently discontinue of study treatment
Thrombocytosis	
Grade 1, no evidence of clinical thrombosis and platelet counts < 1,000K	Maintain dose and current monitoring plan

Grade 2, no evidence of clinical thrombosis and platelet count ≥ 1,000K	Suspend dose until resolved to Grade ≤1 or baseline If not resolved by 14 days, then obtain hematology consultation If not resolved after 21 days, then permanently discontinue study treatment
Grade 3 or Grade 4, evidence of clinical thrombosis event	Suspend dose and permanently discontinue patient from study treatment
Investigations	
Serum creatinine	
Grade 1	Maintain dose
Grade 2	Suspend dose until resolved to Grade ≤1 or baseline If not resolved after 21 days, this discontinue of study treatment
Grade 3 or Grade 4	Suspend dose and permanently discontinue patient from study treatment
Bilirubin ^b	
Grade 1	Maintain dose
Grade 2	Suspend dose until resolved to Grade ≤ 1 or baseline
	If not resolved after 21 days then discontinue of study treatment
Grade 3	Suspend dose until resolved to Grade ≤ 1 or baseline, then:
Grade 4	Suspend dose and discontinue patient from study treatment
AST or ALT	
Grade 1	Maintain dose
Grade 2 and bilirubin < CTCAE grade 2	Maintain dose
Grade 2 and bilirubin ≥ CTCAE grade 2	Suspend dose until resolved to Grade ≤ 1 or baseline If not resolved after 21 days , then discontinue of study treatment
Grade 3	Suspend dose until resolved to Grade ≤ 1 or baseline
	If not resolved after 21 days, then discontinue of study treatment
Grade 4	Suspend dose and discontinue patient from study treatment
Amylase and/or lipase ele	vation
Grade 1	Maintain dose
Grade 2	Maintain dose
Grade 3 with clinical signs or symptoms of pancreatitis	Suspend dose until resolved to ≤ Grade 2, then:
Grade 4	Suspend dose and discontinue patient from study treatment
Gastro intestinal disorders	
Vomiting	
Grade 1	Maintain dose
Grade 2	Maintain dose

Grade 3	Suspend dose (only if vomiting cannot be controlled with optimal anti- emetic treatments) until resolved to Grade ≤ 1
	If not resolved after 14 days, then discontinue of study treatment
Grade 4	Suspend dose and discontinue patient from study treatment
Diarrhea	
Grade 1 or 2	Maintain dose
Grade 2	Suspend dose (only if diarrhea cannot be controlled with optimal anti- diarrhea treatments) until resolved to ≤ Grade 1
	If not resolved after 14 days, then discontinue of study treatment
Grade 3	Suspend dose (only if diarrhea cannot be controlled with optimal anti- diarrhea therapy) until resolved to Grade ≤ 1
	If not resolved after 14 days, then discontinue of study treatment
Grade 4	Suspend dose and discontinue patient from study treatment
Ulceration	
Grade 1	Maintain dose
Grade 2	Suspend dose until resolved to Grade ≤ 1, then
	If not resolved after 21 days , then discontinue of study treatment
Grade 3 or Grade 4	Suspend dose and permanently discontinue patient from study treatment
Hemorrhage	T
Grade 1	Maintain dose
Grade 2	Suspend dose until resolved to Grade ≤ 1
	If not resolved after 21 days , then permanently discontinue of study treatment
Grade 3 or Grade 4	Suspend dose and permanently discontinue patient from study treatment
Cardiac Disorders	
Clinically significant increase in cardiac enzymes (Troponin and NTproBNP)	Recommendation: Repeat test within 1 week. If it remains elevated get pediatric cardiology consult, perform echocardiogram and ECG if not already done. Continuing study treatment should be done in consultation with a pediatric cardiologist. Manage per standard of care Continue checking Troponin/NTproBNP levels at a frequency determined by the cardiologist and investigator until resolution.
Grade 1	Maintain dose
Asymptomatic Grade 2	Maintain dose
Symptomatic Grade 2	Suspend dose until resolved to Grade ≤ 1 or baseline If not resolved after 21 days, then permanently discontinue of study treatment
Symptomatic Grade 3	Suspend dose until resolved to ≤ Grade 1 or baseline
with history of asymptomatic grade 2	If not resolved after 21 days, then permanently discontinue of study treatment

Grade 3 – if Grade 2 was symptomatic	Suspend dose and permanently discontinue patient from study treatment
Grade 4	Suspend dose and discontinue permanently patient from study treatment
Hypertension	
Grade 1	Maintain dose
Grade 2	Suspend dose until resolved to Grade ≤ 1 or baseline (with or without HTN monotherapy)
	If not resolved with 21 days, then permanently discontinue of study treatment
Grade 3	Suspend dose until resolved to ≤ Grade 2, (with or without HTN monotherapy),
	If two agents required for control, Suspend dose and discontinue patient from study treatment
Grade 4	Suspend dose and permanently discontinue patient from study treatment
Other adverse events	
Grade 1 or 2	Maintain dose
Grade 3	Suspend dose until resolved to Grade ≤ 1 or baseline, then↓ 1 dose level
Grade 4	Suspend dose and discontinue permanently patient from study drug treatment

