2.2 Secondary objective(s)

Objective	Endpoint		
Part 1, Part 2, Part 3:	Part 1, Part 2, Part 3:		
 To evaluate branaplam pharmacokinetics in plasma after single and repeated doses of branaplam. 	AUC and Cmax of branaplam		
To evaluate the effect of branaplam on growth parameters	 Growth measurements (body weight, head circumference, length and chest circumference) 		
To evaluate the effect of branaplam on respiratory function	 Pulse oximetry, respiratory rate, paradoxical breathing assessment, chest circumference during quiet breathing. 		

Objective	Endpoint
To evaluate the effect of branaplam on infant motor development.	 CHOP INTEND infant motor scale up to age of 36 months
	Hammersmith Infant Neurologic Examination
• In addition to the above for Part 2:	 In addition to the above for Part 2:
To evaluate the efficacy of branaplam on motor and developmental milestones	Preservation of oral feeding
To evaluate the efficacy of branaplam on the ability to sit without support.	Ability to sit without support over time as assessed by HINE-2
• In addition to the above for Part 3:	 In addition to the above for Part 3:
 To evaluate the efficacy of branaplam on motor and developmental milestones 	Preservation of oral feeding
To evaluate the efficacy of branaplam on the ability to sit without support.	 Ability to sit without support, stand or walk over time as assessed by HINE-2
To assess the proportion of infants who are alive and are without permanent ventilation over time	Adverse Events and deaths over time
To assess the impact of treatment with branaplam on time-to-event (death, permanent ventilation)	Adverse Events and deaths over time

3 Study design

This is an open-label, multi-part, first-in-human proof of concept study in infants with Type 1 spinal muscular atrophy, to evaluate safety, tolerability, PK, PD and efficacy of oral branaplam. Parts 1, 2 and 3 are intended to be non-confirmatory.

All patients must have confirmed SMA type 1 and 2 copies of the SMN2 gene.

In Part 1 of the study, patients will be dosed once weekly with branaplam. The branaplam dose will be escalated in subsequent cohorts until MTD was determined or when sufficient PK results would not confirm that the MTD could not be reached due to a potential pharmacokinetic exposure plateau at higher doses. Patients will be dosed at least 24 hours apart for the first dose

Protocol No. CLMI070X2201

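### Table 5-7 allows restart at Grade 2 after Grade 3 hypertension, while its own Grade 2 row requires suspension, and it does not say which row then governs

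*Protocol*

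**What the plan says.** Table 5-7 in Protocol Section 5.4.6 gives the criteria for interrupting and restarting branaplam after adverse events possibly related to it. Its first column is headed "Worst toxicity CTCAE Grade" and its second "7 days post dose administration (including day of administration".

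The two hypertension rows at issue are:

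- **Grade 2:** the instruction is "Suspend dose until resolved to Grade ≤ 1 or baseline (with or without HTN monotherapy". The row goes on to end treatment for good when the child has not recovered in that sense by day 21.
- **Grade 3:** the instruction is "Suspend dose until resolved to ≤ Grade 2, (with or without HTN monotherapy". The row also takes the child off treatment when control needs a second agent. No time limit is stated.

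Nothing else in Section 5.4.6, including the table's footnotes and the paragraphs after it, links the two rows or says what happens when an event moves from one grade to the other.

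Section 8.1.1 lists the adverse events and toxicities covered by Table 5-7 among the circumstances in which study treatment must be discontinued. The same list ends with an exception: where there is perceived benefit, continuation may be considered after discussion with the sponsor, the investigator and the DMC. Section 5.4.6 has a similar provision that depends on the sponsor's agreement.

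**The concern.** A restart threshold should normally lead to a state in which dosing is permitted. Here the Grade 3 row releases a child at Grade 2, and the row above treats Grade 2 as a reason to withhold the drug and, after 21 days, to stop it for good. Two sites with the same patient could reach different decisions, and each could cite the table.

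Two things are at stake.

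- **Patient safety.** Hypertension is among the SUSAR terms listed in Sections 1.1.1 and 3.8. Section 3.8 relies on adherence to the stopping rules in its general text and in its nerve and renal paragraphs, and on blood pressure monitoring, among other measures, for cardiac risk. Sites cannot adhere closely to a rule whose scope is unclear.
- **Interpretation of the primary objective.** Safety and tolerability is a primary objective in all three parts, and SAP Section 2.8.2 tabulates treatment-emergent events leading to permanent discontinuation. For hypertension that count would depend partly on which row a site applied.

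**Working it through.** No figure in the plan is involved, so the check is a reading of the rows side by side.

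**Step 1: the two rows compared.**

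| Item | Grade 2 row | Grade 3 row |
|---|---|---|
| Immediate action | Suspend | Suspend |
| Grade at which dosing may resume | 1 or lower, or baseline | 2 or lower |
| Time limit | 21 days, then permanent stop | None stated |
| Antihypertensive treatment | With or without one agent | With or without one agent; two agents means discontinuation |

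The single-agent wording is in both rows, so it does not separate the cases. On restart grade and time limit the Grade 3 row is looser. On number of agents it is stricter, because only that row has a two-agent trigger.

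**Step 2: follow one child.** Take a Grade 3 event possibly related to study drug that falls to Grade 2 on no agent or one agent and stays there. The Grade 3 row's restart condition is met. What follows depends on how the row is selected:

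- *Worst grade over the whole event.* The Grade 3 row continues to govern. Dosing goes on at Grade 2 with no stated limit.
- *Worst grade in the 7 days after each dose.* Section 3 states for Part 1 that "patients will be dosed once weekly with branaplam", and Parts 2 and 3 are also weekly, so each dose opens a new 7-day window. After restart the worst grade in the new window is 2. The Grade 2 row requires suspension and then a permanent stop after 21 days, a period of 21 / 7 = 3 weekly dosing intervals.
- *Current grade.* The Grade 2 row applies once the event falls to Grade 2, and the restart permitted by the Grade 3 row never takes effect.

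The readings end in continued dosing, in suspension after restart with possible permanent discontinuation, or in no restart at all. The table does not choose between them.

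**Step 3: compare the other toxicities in Table 5-7.** Only one other toxicity allows restart from Grade 3 at Grade 2: amylase or lipase elevation with signs of pancreatitis, "Suspend dose until resolved to ≤ Grade 2, then". Its Grade 2 action is to maintain the dose, so those rows fit together. In the neighbouring cardiac block, symptomatic Grade 2 and the Grade 3 case that may restart both require Grade 1 or baseline within 21 days, so those also fit. Hypertension is the only toxicity in the table whose Grade 3 restart grade is one that its own Grade 2 row suspends.

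The missing time limit is not unique, since the Grade 3 bilirubin row also lacks one. The mismatch in restart grade is.

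**The case against.** The strongest defence is that rows are chosen by worst grade. A child whose event peaked at Grade 3 is under the Grade 3 row when restart is decided, so the Grade 2 row does not compete at that moment. In the text as read from the PDF, the 7-day phrase heads the action column and not the grade column. Section 9.1.1 follows an adverse event to resolution with changes in severity noted. An unresolved event could therefore be said to keep its worst grade of 3.

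Part of this stands. A reader might infer that the two rows give opposite orders at the same instant. The documents do not establish that, because under worst-grade selection only the Grade 3 row is in play when restart is decided. The defence does not settle what governs after restart, since the table never says that a Grade 3 event keeps its row, and the windowed reading is equally available.

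Three other inferences go too far:

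- **That the same blood pressure is treated in opposite ways.** The documents do not define the hypertension grades; they defer to the current CTCAE. Only the grade can be compared.
- **That the worse event has the more permissive rule overall.** The two-agent trigger makes the Grade 3 row stricter in one respect.
- **That every child passing from Grade 3 to Grade 2 is affected.** The table applies only where there is no clear explanation other than possible drug effect. Unrelated Grade 1 to 3 events are left to the investigator, children needing two agents are discontinued, and events in several organs follow a separate rule.

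The exceptions in Sections 5.4.6 and 8.1.1 also mean that a site need not decide alone. They allow a case-by-case departure but do not say what the default rule is.

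**Conclusion.** The inconsistency is real and limited. For hypertension possibly related to study drug and controlled with at most one agent, a child restarted at CTCAE Grade 2 after a Grade 3 event is in a state for which the adjacent row requires suspension. Neither the governing row nor the application of the 21-day limit is stated. The conclusion rests on the row wording alone and on no assumption about blood pressure values.

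Its frequency cannot be estimated. Hypertension appears among the SUSAR terms without a grade, Section 1.1.1 reports no SUSARs in Part 3, and enrolment is closed with patients now in Part 3. The point still merits correction, because 8.1.1 makes Table 5-7 the basis for required discontinuation in an ongoing part with no defined end. No view is taken here on which threshold is clinically right.

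**What to change.** Reconcile the Grade 2 and Grade 3 hypertension rows of Table 5-7. The reconciled text should state:

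- which row applies to a child restarted at Grade 2 after a Grade 3 event; and
- whether a time limit applies in that situation.

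The sponsor, its cardiology advisers and the DMC should decide the content. If the outcome is meant to depend on the earlier grade, the table can say so, as the cardiac rows already do. The cost is one table correction in an amendment or clarification letter, with no change to assessments or data collection.

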5.4.7 Within-patient dose escalation

In Part 2 and Part 3 of the study no intra-patient dose escalation was planned. However, the potential loss of a positive effect over time of the starting dose may occur. Loss of effect is defined as loss of previously obtained motor skills from baseline, independent of ventilation of at least 2 points on the HINE Section 2, excluding voluntary grasp and/or more of five points on the CHOP-INTEND scale for two consecutive assessments. On the other hand, if decline of assessment occurred during an acute illness episode this would not be considered a loss of effect.

Pulmonary events or loss of feeding will not be considered as loss of effect since these will not be distinguishable for normal disease progression without efficacy.

After the 52-weeks analysis for Part 2, a comparison of the two doses showed 2.5 mg/kg to have numerically better changes in HINE-2 scores compared to 0.625 mg/kg following one year of treatment, and with comparable safety profiles. It is expected that the higher dose (2.5mg/kg) will maximize the potential long-term benefit which participating patients may be switched to as a selected optimal dose in Part 3 of the study.

The decisions will be made jointly by the investigator and Sponsor, with consultation by the independent DMC.

